13.2.1 Efficacy Assessments

Tumor evaluations for the purposes of the primary endpoint are made based on RECIST criteria (Therasse, 2000), New Guidelines to Evaluate the Response to Treatment in Solid Tumors, *Journal of National Cancer Institute*, Volume 92; pages 205–216 and revised RECIST guidelines (version 1.1) (Eisenhauer, 2009).

13.2.2 Definitions of Measurable and Non-Measurable Disease

Measurable disease represents the presence of at least 1 measurable nodal or non-nodal lesion. If the measurable disease is restricted to a solitary lesion, its neoplastic nature should be confirmed by cytology/histology.

Measurable lesions (both nodal and non-nodal): The minimum size of a measurable, non-nodal target lesion at Baseline should be no less than double the slice thickness or 10 mm, whichever is greater, eg, the minimum non-nodal lesion size for CT/MRI with 5 mm cuts will be 10 mm).

Lytic bone lesions or mixed lesions with identifiable soft tissue components that can be evaluated by CT/MRI can be considered as measurable lesions, if the soft tissue component meets the definition of measurability. Measurable nodal lesions (ie, lymph nodes), lymph nodes ≥ 15 mm in short axis can be considered for selection as target lesions. Lymph nodes measuring ≥ 10 mm and < 15 mm are considered non-measurable. Lymph nodes smaller than 10 mm in short axis at Baseline, regardless of the slice thickness, are normal and not considered indicative of disease.

Cystic lesions thought to represent cystic metastases can be considered as measurable lesions, if they meet the definition of measurability described above. Simple cysts with non-enhancing walls and low CT density are not considered malignant lesions unless proven by biopsy.

Non-measurable lesions: All other lesions are considered non-measurable, including small lesions (eg, longest diameter < 10 mm with CT/MRI or pathological lymph nodes with ≥ 10 to < 15 mm short axis), as well as truly non-measurable lesions eg, blastic bone lesions, ascites, pleural/pericardial effusion and inflammatory breast disease.

13.2.3 Methods of Tumor Measurement

All measurements should be taken and recorded in metric notation (mm), using a ruler or calipers. All baseline evaluations should be performed as closely as possible to the beginning of treatment and never more than 4 weeks before the beginning of the treatment. Imaging-based evaluation is preferred to evaluation by clinical examination when both methods have been used to assess the anti-tumor effect of a treatment. For optimal evaluation of patients, the same methods of assessment and technique should be used to assess each reported lesion at Baseline and during Follow-up. Contrast-enhanced CT of chest, abdomen, and pelvis should preferably be performed using a 5-mm slice thickness. If a patient is known to have a medical contraindication to CT contrast or develops a contraindication during the trial, the following change in imaging modality will be accepted for follow-up: a non-contrast CT of chest (MRI not recommended due to respiratory artifacts) plus contrast-enhanced MRI of abdomen and pelvis.

13.2.3.1 Other Tumor Response Considerations

Fluorodeoxyglucose-positron emission tomography, endoscopy, and laparoscopy: The utilization of positron emission tomography imaging, endoscopy, and laparoscopy for objective tumor evaluation has not yet been fully and widely validated. The utilization of such techniques for objective tumor response should be restricted to validation purposes in specialized centers; however, such techniques can be useful in confirming complete pathological response when biopsies are obtained.

Cytology and histology: Cytology and histology can be used to differentiate between partial response (PR) and complete response (CR) in rare cases (ie, after treatment to differentiate between residual benign lesions and residual malignant lesions in tumor types such as germ cell tumors).

Clinical examination: Clinical lesions will only be considered measurable when they are superficial (ie, skin nodules and palpable lymph nodes). Documentation by color photography is recommended for the case of skin lesions, including a ruler to estimate the size of the lesion. Clinical disease progression is acceptable and wherever possible, should be confirmed by imaging studies.

13.2.4 Definitions of Target and Non-Target Lesions

For the evaluation of lesions at Baseline and throughout the study, the lesions are classified at Baseline as either target or non-target lesions.

Target Lesions: All measurable lesions (nodal and non-nodal) up to a maximum of 5 lesions in total (and a maximum of 2 lesions per organ), representative of all involved organs, should be identified as target lesions and recorded and measured at Baseline. Target lesions should be

selected based on their size (lesions with the longest diameter) and their suitability for accurate repeated measurements (either by imaging techniques or clinically).

Each target lesion must be uniquely and sequentially numbered on the eCRF (even if it resides in the same organ). A sum of diameters (long axis for non-nodal lesions, short axis for nodal) for all target lesions will be calculated and reported as the baseline sum of diameters. The baseline sum of diameters will be used as reference by which to characterize the objective tumor response. Each target lesion identified at Baseline must be followed at each subsequent evaluation and documented on eCRF.

Non-Target Lesions: All other lesions are considered non-target lesions, ie, lesions not fulfilling the criteria for target lesions at Baseline. Presence or absence or worsening of non-target lesions should be assessed throughout the study; measurements of these lesions are not required.

Multiple non-target lesions involved in the same organ can be assessed as a group and recorded as a single item (ie, multiple liver metastases). Each non-target lesion identified at Baseline must be followed at each subsequent evaluation and documented on eCRF.

13.2.5 Determination of Target Lesion Response

Table 13-2: Response Criteria for Target Lesions

Response Criteria	Evaluation of Target Lesions
Complete response	Disappearance of all non-nodal target lesions. In addition, any pathological lymph nodes assigned as target lesions must have a reduction in short axis to < 10 mm ^a
Partial response	At least a 30% decrease in the sum of diameter of all target lesions, taking as reference the baseline sum of diameters
Progressive disease	At least a 20% increase in the sum of diameter of all measured target lesions, taking as reference the smallest sum of diameter of all target lesions recorded at or after Baseline. In addition to the relative increase of 20%, the sum must also demonstrate an absolute increase of at least 5 mm ^b
Stable disease	Neither sufficient shrinkage to qualify for partial response or complete response nor an increase in lesions which would qualify for progressive disease

- a. Sum of diameters for complete response may not be 0 when nodal lesions are part of target lesions.
- b. Following an initial complete response, progressive disease cannot be assigned if all non-nodal target lesions are still not present and all nodal lesions are < 10 mm in size. In this case, the target lesion response is complete response.

Notes on Target Lesion Response

Lesions split: In some circumstances, disease that is measurable as a target lesion at Baseline and appears to be 1 mass can split to become 2 or more smaller sub-lesions. When this occurs, the diameters (long axis — non-nodal lesion, short axis - nodal lesions) of the 2 split lesions should be added together and the sum recorded in the diameter field on the electronic case report form under the original lesion number. This value will be included in the sum of diameters when deriving target lesion response. The individual split lesions will not be considered as new lesions, and will not automatically trigger a PD designation

Lesions coalesced: Conversely, it is also possible that 2 or more lesions, which were distinctly separate at Baseline, become confluent at subsequent visits. When this occurs, a plane between the original lesions may be maintained that would aid in obtaining diameter measurements of each individual lesion. If the lesions have truly coalesced such that they are no longer separable, the maximal diameters (long axis — non-nodal lesion, short axis - nodal lesions) of the “merged lesion” should be used when calculating the sum of diameters for target lesions. On the electronic case report form, the diameter of the “merged lesion” should be recorded for the size of 1 of the original lesions while a size of “0” mm should be entered for the remaining lesion numbers which have coalesced.

13.2.6 Determination of Non-Target Lesion Response

Table 13-3: Response Criteria for Non-Target Lesions

Response Criteria	Evaluation of Non-Target Lesions
Complete Response	Disappearance of all non-target lesions. In addition, all lymph nodes assigned a non-target lesion must be non-pathological in size (< 10 mm short axis)
Progressive Disease	Unequivocal progression of existing non-target lesions ^a
Non-complete response / Non-progressive disease	Neither complete response nor progressive disease

a. Although a clear progression of non-target lesions only is exceptional, in such circumstances, the opinion of the treating physician does prevail, and the progression status should be confirmed later on by the central review.

Non-Target Lesion Response

The response for non-target lesions is CR only if all non-target, non-nodal lesions that were evaluated at Baseline are now all absent and all non-target nodal lesions returned to normal size

(ie, < 10 mm). If any of the non-target lesions are still present, or there are any abnormal nodal lesions (ie, ≥ 10 mm), the response can only be “Non-CR/Non-PD.”

Unequivocal progression: To achieve “unequivocal progression” on the basis of non-target disease there must be an overall level of substantial worsening in non-target disease such that, even in presence of CR, PR, or SD in target disease, the overall tumor burden has increased sufficiently to merit discontinuation of therapy. In order for a PD to be assigned on the basis of non-target lesions, the increase in the extent of the disease must be substantial even in cases where there is no measurable disease at Baseline

New Lesions

The appearance of a new lesion is always associated with PD and has to be recorded as a new lesion in the eCRF.

- If a new lesion is equivocal, for example because of its small size, continued therapy and follow-up evaluation will clarify if it represents truly new disease. If repeat scans confirm there is definitely a new lesion, then progression should be declared using the date of the first observation of the lesion
- If new disease is observed in a region which was not scanned at Baseline or where the particular baseline scan is not available for some reason, then this should be considered PD
- A lymph node is considered as a “new lesion” and therefore, indicative of PD if the short axis increases in size to ≥ 10 mm for the first time in the study plus 5 mm absolute increase

13.2.7 Evaluation of Overall Lesion Response

The evaluation of overall lesion response at each assessment is a composite of the target lesion response, non-target lesion response, and presence of new lesions as shown below in [Table 13-4](#).

Table 13-4: Overall Lesion Response at Each Assessment (RECIST v1.1)

Target Lesions	Non-target Lesions	New Lesions	Overall Lesion Response
CR	CR	No	CR ^a
CR	Non-CR/Non-PD	No	PR
PR	Non-PD	No	PR ^a
SD	Non-PD	No	SD ^{a,b}

Target Lesions	Non-target Lesions	New Lesions	Overall Lesion Response
PD	Any	Yes or No	PD
Any	PD	Yes or No	PD
Any	Any	Yes	PD

CR = complete response; PD = progressive disease; PR = partial response; RECIST = Response Evaluation Criteria in Solid Tumors; SD = stable disease.

- a. This overall lesion response also applies when there are no non-target lesions identified at Baseline.
- b. Once confirmed PR was achieved, all these assessments are considered PR.

13.3 Bayesian Logistic Regression Model

This section (along with [Section 6.10](#)) describes the Bayesian Logistic Regression Model (BLRM) used to make dose recommendations during Phase I.

13.3.1 Specification

See [Section 6.12](#) for DLT definitions and [Section 6.10.2](#) for definitions of DLT-evaluable patients for inclusion in the DDS.

After each cohort of patients, the posterior distributions for the probabilities of DLT rates at different dose levels will be obtained. Dose recommendation will be based on the probability that the true DLT rate for each dose lies in 1 of the following categories in [Table 13-5](#).

Table 13-5: Toxicity Categories

Name	Lower Limit	Upper Limit
Under dosing	0%	< 16%
Target toxicity	16%	< 33%
Excessive toxicity	33%	100%

The N-CRM model will predict rates of toxicity for doses between 1 mcg and 200 mcg. This is the limit that has been identified for the purposes of the simulations. For ease of presentation, summaries of the state of the N-CRM model will collapse these 1 mcg dose increments into bands as follows:

- Between 1 mcg and 9 mcg: no collapsing
- Between 10 mcg and 18 mcg: in increments of 2 mcg
- Between 20 mcg and 200 mcg: in increments of 5 mcg

Note: If IPE proceeds to a target dose of >150 mcg according to BLMR output and treatment at this dose level is well-tolerated, then an additional BLMR that allows for a maximum target dose of up to 350 mcg will be constructed. This model will be specific to the dose-toxicity relationship of target doses following IPE. The prior distribution for this new model and pseudo-patient information will consider posterior distributions from the existing BLMR(s). Operating characteristics will be assessed from a series of simulations to be summarized in a simulation report.

In case of changes in dosing schedule during dose escalation, a BLRM of the same functional form will be used to estimate the dose-DLT relationship for each schedule based on a newly derived “Bayesian prior” incorporating the historical trial data and the on-study data from previous schedule. Each time the model is updated, all available information on the dose-DLT relationship from all explored dosing schedules will be used. To account for between schedule variability in the assessment of a given dosing schedule, the DLT data obtained from other explored dosing schedules will be down-weighted.

Escalation Rule

Let d^* be the highest dose at which the DLT status of at least 3 patients is known. A dose is cleared if the ratio between it and d^* is less than or equal to 3.34. A dose is eligible if it is both cleared and the current posterior estimate of the probability that it lies in the excessive toxicity band is less than 0.25 [the EWOC rule]. The dose recommended by the N-CRM will be the eligible dose currently with the highest posterior probability of being in the target toxicity band.

Futility Rule

There will be no futility rule. Phase I cohorts will continue to enroll until either the MTD (or RP2D) is identified or the Sponsor terminates the study for other reasons.

Success Rule

The N-CRM model will recommend that enrollment to Phase I cohorts should stop once either (a) at least 6 evaluable patients have been treated in the dose range in which the MTD is currently thought to lie or (b) no dose is eligible for dosing because of the EWOC rule. The Sponsor reserves the right to continue enrollment in the Phase I cohorts beyond this time if it is considered clinically useful so to do.

Enrollment Limit

There will be no enrollment limit. Enrollment will be open.

Dose-toxicity Model

X-hats:

Let $d_i = i$ mcg, $i=1, \dots, 200$. Let \hat{x}_i denote the nominal dose used in the dose-toxicity model that corresponds to d_i . Let $d_{ref} = 0$ mcg. Then $\hat{x}_i = d_i - d_{ref} = d_i$.

Functional Form:

Let Y_j be a Bernoulli random variable indicating whether the j^{th} patient experiences a DLT ($Y_j=1$) or not ($Y_j=0$). Let \hat{x}_{ij} denote the nominal dose received by the j^{th} patient. The BLRM will model the probability that the j^{th} patient experiences a DLT as

$$p(Y_j = 1 | \hat{x}_{ij}, \alpha, \beta, \{(\hat{x}_{ik}, y_k); k = 1, \dots, j-1\}) = \frac{e^{\alpha + \beta \hat{x}_{ij}}}{1 + e^{\alpha + \beta \hat{x}_{ij}}}$$

The Prior:

The dose-toxicity model is a logistic model and takes the form:

$$\text{logit}(p) = \alpha + \beta \hat{x}$$

It is assumed that toxicity increases with increasing dose and thus the slope, β , must be greater than 0. This assumption is implemented in the model by estimating γ where $\gamma = \ln(\beta)$. The prior for α and γ takes the form

$$[\alpha] \sim MVN \left(\begin{bmatrix} \mu_\alpha \\ \mu_\gamma \end{bmatrix}, \begin{bmatrix} \sigma_\alpha \times \sigma_\alpha & \rho \times \sigma_\alpha \times \sigma_\gamma \\ \rho \times \sigma_\alpha \times \sigma_\gamma & \sigma_\gamma \times \sigma_\gamma \end{bmatrix} \right)$$

Initial values for μ_α , μ_β , σ_α , σ_β and ρ were based on the results of simulation study (on file at PPD) and are given in [Table 13-6](#).

Table 13-6: Initial Values for BLRM Simulation

Parameter	Initial Value
μ_α	-2.95
μ_β	-5
σ_α	2.75
σ_β	2.75
ρ	0

BLRM = Bayesian Logistic Regression Model.

Bayes' Theorem will be used to update the values of μ_α , μ_β , σ_α , σ_β and ρ (and hence the probabilities of toxicity and toxicity band membership for each dose) after the results of each cohort of patients are known.

The pseudo-patient information in [Table 13-7](#) was also included as prior information.

Table 13-7: Pseudo-Patient Information

Dose	Number of Patients	Number of DLTs
3	1	0.1
10	1	0.125
30	1	0.15
100	1	0.3
135	1	0.4
200	1	0.5

DLT = dose-limiting toxicity.

This prior gives rise to the probabilities of toxicity and band membership for selected doses as shown in Table 13-8.

Table 13-8: Prior Probabilities

Dose	p(Toxicity)	Probability that Dose is in Toxicity Band:		
		Under Dosing	Target Toxicity	Excess Toxicity
3 mcg	0.109	0.765	0.156	0.079
10 mcg	0.118	0.742	0.169	0.089
20 mcg	0.136	0.697	0.184	0.119
40 mcg	0.186	0.620	0.187	0.193
80 mcg	0.268	0.539	0.170	0.290
100 mcg	0.297	0.512	0.165	0.323
140 mcg	0.343	0.471	0.157	0.372
180 mcg	0.378	0.441	0.148	0.412

The dose recommended by the N-CRM model will be subject to clinical review. The SST may select the recommended dose or a lower dose.

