13.3.3 Sample Paths

The tables in this section ([Table 13-9](#), [Table 13-10](#), [Table 13-11](#), and [Table 13-12](#)) illustrate various possible paths of dose recommendation and state of the N-CRM model given various response patterns that might be observed in the study.

Table 13-9: Scenario 1, No DLT Reported at Any Dose

Dose (mcg)	Number of DLTs / Number of Patients Treated	Estimated MTD	Recommended Next Dose
3	0 / 3	38	10
10	0 / 3	67	30
30	0 / 3	185	100
100	0 / 3	198	195
195	0 / 3	>200	200

DLT = dose-limiting toxicity; MTD = maximum tolerated dose.

Table 13-10: Scenario 2, One DLT Reported at 30 mcg Dose

Dose (mcg)	Number of DLTs / Number of Patients Treated	Estimated MTD	Recommended Next Dose
3	0 / 3	38	10
10	0 / 3	67	30
30	1 / 3	185	100
25	0 / 3	35	35
35	0 / 3	77	75
75	0 / 3	148	145
145	0 / 3	>200	200
200	0 / 3	>200	200
200	0 / 3	>200	Stop

DLT = dose-limiting toxicity; MTD = maximum tolerated dose.

Table 13-11: Scenario 3, Two DLTs Reported at 100 mcg Dose

Dose	Number of DLTs / Number of Patients Treated	Estimated MTD	Recommended Next Dose
3	0 / 3	38	10
10	0 / 3	67	30
30	0 / 3	185	100
100	2 / 3	61	60
60	0 / 3	70	70
70	0 / 3	78	75
75	0 / 3	87	85
85	0 / 3	100	100
100	2 / 3	83	80
80	0 / 3	87	85
85	0 / 3	91	90
90	0 / 3	97	Stop

DLT = dose-limiting toxicity; MTD = maximum tolerated dose.

Table 13-12: Scenario 4, One DLT at 30 mcg, 2 DLTs at 145 mcg and 2 DLTs at 100 mcg Dose

Dose	Number of DLTs / Number of Patients Treated	Estimated MTD	Recommended Next Dose
3	0 / 3	38	10
10	0 / 3	67	30
30	0 / 3	28	25
25	1 / 3	35	35
35	0 / 3	77	75
75	0 / 3	148	145
145	2 / 3	87	85
85	0 / 3	99	95
95	0 / 3	109	105
105	2 / 3	93	90
90	0 / 3	99	Stop

DLT = dose-limiting toxicity; MTD = maximum tolerated dose.

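### The prior printed in Protocol Tables 13-6 and 13-7 does not produce Table 13-8 or several sample-path rows, and Tables 13-10 and 13-12 contain conflicting entries

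*Protocol*

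**What the plan says.** Section 13.3.1 of the protocol specifies a two-parameter logistic model, linear in dose in mcg because the reference dose is zero. The intercept and the log of the slope have a bivariate normal prior. Table 13-6 gives means of -2.95 and -5, both sigmas 2.75, and correlation 0. The covariance matrix is written with sigma times sigma on the diagonal, so 2.75 is a standard deviation. Table 13-7 lists six pseudo-patients, and the text says this information "was also included as prior information". Then: "This prior gives rise to the probabilities of toxicity and band membership for selected doses as shown in Table 13-8".

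A dose is eligible if it is at most 3.34 times the highest dose with at least three patients of known DLT status and its probability of excessive toxicity (a DLT rate of 33% or more) is below 0.25. The choice among eligible doses is fixed: "The dose recommended by the N-CRM will be the eligible dose currently with the highest posterior probability of being in the target toxicity band".

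Section 13.3.3 illustrates the rule in four paths:

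- "Table 13-9: Scenario 1, No DLT Reported at Any Dose"
- "Table 13-10: Scenario 2, One DLT Reported at 30 mcg Dose"
- "Table 13-11: Scenario 3, Two DLTs Reported at 100 mcg Dose"
- "Table 13-12: Scenario 4, One DLT at 30 mcg, 2 DLTs at 145 mcg and 2 DLTs at 100 mcg Dose"

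For a further model covering intra-patient escalation (IPE) target doses, Section 13.3.1 says: "The prior distribution for this new model and pseudo-patient information will consider posterior distributions from the existing BLMR(s").

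**The concern.** Section 13.3 is the protocol's written specification of its overdose control in a first-in-human trial, and SAP Section 14.1 refers readers back to it. If the prior and its stated output disagree, a reader cannot tell which model governed escalation, or which model the operating characteristics in Section 13.3.2 describe.

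The mismatch matters where the model, not the 3.34-fold cap, decides the dose. On the no-DLT path the first such step comes after 100 mcg. Section 1.4 reports the trial at that point: 3 patients at 100 mcg and no DLT. The notes to Figure 6-3 in Section 6.10.1 repeat 195 mcg as the model's recommendation there. The posterior of this model is also meant to inform the prior of the later IPE model.

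**Working it through.** **Inputs (all Section 13.3.1).** With a the intercept and g the log slope: logit(p) = a + exp(g) × dose; a ~ N(-2.95, 2.75²); g ~ N(-5, 2.75²); correlation 0. Pseudo-patients: one each at 3, 10, 30, 100, 135 and 200 mcg, with 0.1, 0.125, 0.15, 0.3, 0.4 and 0.5 DLT. Bands: under-dosing below 16%, target 16% to below 33%, excessive 33% and above.

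**Method.** Posterior weight ∝ normal prior × Π p^y (1-p)^(n-y), with pseudo-patients entered as fractional outcomes (n = 1). I integrated over a grid of at least 1,201 points per axis for Table 13-8. A Monte Carlo check agreed within about 0.002.

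**Step 1: Table 13-8** (computed / printed)

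| Dose (mcg) | Mean p(tox) | Target band | Excess band |
|---|---|---|---|
| 3 | 0.166 / 0.109 | 0.284 / 0.156 | 0.131 / 0.079 |
| 10 | 0.170 / 0.118 | 0.292 / 0.169 | 0.136 / 0.089 |
| 20 | 0.176 / 0.136 | 0.303 / 0.184 | 0.144 / 0.119 |
| 40 | 0.190 / 0.186 | 0.327 / 0.187 | 0.164 / 0.193 |
| 80 | 0.228 / 0.268 | 0.365 / 0.170 | 0.233 / 0.290 |
| 100 | 0.252 / 0.297 | 0.368 / 0.165 | 0.284 / 0.323 |
| 140 | 0.307 / 0.343 | 0.336 / 0.157 | 0.394 / 0.372 |
| 180 | 0.364 / 0.378 | 0.293 / 0.148 | 0.482 / 0.412 |

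Of the 32 printed cells (these 24 plus under-dosing), one agrees within 0.01: mean p(tox) at 40 mcg. The largest gap is under-dosing at 180 mcg, 0.441 - 0.224 = 0.217.

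**Step 2: other readings of the prior.** Largest gap to Table 13-8:

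- SD 2.75 without pseudo-patients: 0.217.
- 2.75 as a variance, with pseudo-patients: 0.224.
- 2.75 as a variance, without pseudo-patients: 0.037, with 8 of 32 cells within 0.01.
- Log-dose scales: 0.18 to 0.32.

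None matches to the three decimals printed. The 0.037 reading contradicts both Table 13-7 and the covariance matrix.

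**Step 3: conflicts visible without a model.**

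- 0/3 at each of 3, 10 and 30 mcg gives estimated MTD 185 and next dose 100 in Tables 13-9 and 13-11, but 28 and 25 in Table 13-12.
- Table 13-10 prints 185 and 100 after 1/3 at 30 mcg, yet its next row is 25 mcg.
- The Table 13-12 heading places DLTs at 30 and 100 mcg (besides 145). Its rows place them at 25 and 105 mcg.

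These look like displaced cells and do not by themselves imply a second model.

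**Step 4: path rows under the written prior and rule.** The caps are 3 × 3.34 = 10.02, 10 × 3.34 = 33.4, 30 × 3.34 = 100.2 and 100 × 3.34 = 334 (beyond the 200 mcg range).

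| Data so far | Highest dose with P(excess) < 0.25 | Rule's choice | Printed next dose |
|---|---|---|---|
| 0/3 at 3 | 122 | 10 (cap) | 10 |
| and 0/3 at 10 | 134 | 33 (cap) | 30 |
| and 0/3 at 30 | 142 | 100 (cap) | 100 |
| and 0/3 at 100 (Table 13-9) | 175 | about 140 | 195 |
| 0/3 at 3, 10, 30; 2/3 at 100 (Table 13-11) | 87 | about 79 | 60 |
| and 0/3 at 60 (Table 13-11) | 97 | about 87 | 70 |

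The first three rows agree because the cap decides them. In the fourth, P(excess) at 195 mcg is 0.304. With the Section 1.4 patients instead (0/4, 0/3, 0/5, 0/3, assumed all DLT-evaluable), the limit is 174 and P(excess) at 195 mcg is 0.308.

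If the Table 13-10 slip is repaired so that 1/3 at 30 mcg leads to 25, the written prior gives about 86, with a limit of 113. That comparison depends on the repair.

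**The case against.** The strongest reply concerns consequence, since the arithmetic is not in dispute.

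First, SAP Table 1 shows that the trial did not go from 100 to 195 mcg. After 100 mcg fixed came IPE cohorts of 30-100 (n = 5), 30-100-180 (n = 4) and 30-100-300 mcg (6 planned). Suppose those five patients are added as 0/5 at 100 mcg, all evaluable, without DLT and at full weight (none of which the documents state). The written prior then gives P(excess) of about 0.17 at 180 mcg and 0.21 at 195 mcg, both under 0.25. This stands: 0.304 describes the printed path, not the path taken.

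Second, the printed model stops at 200 mcg, so the 300 mcg cohort needed the separate IPE model. SAP Section 14.1 also cites a simulation report and three addendums, which I have not seen. The paths are illustrations, and the Study Safety Team may choose a lower dose than the model recommends. This limits the effect but does not make the prior and its table agree.

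Third, the estimated-MTD column is undefined in the appendix, so differences there are weak evidence; I rely on the next-dose column. The variance reading is not unique either: down-weighting the pseudo-patients brings other variants about as close.

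Finally, the prior formula is damaged on its left side in the extracted text, so a lost superscript in Table 13-6 should be ruled out in the PDF. The legible sigma-times-sigma entries argue against it, and no reading tried reproduces the table.

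**Conclusion.** The concern holds. As written, Tables 13-6 and 13-7 do not generate Table 13-8: 31 of 32 cells differ by more than 0.01, by up to 0.217, and the target-band probability at 100 mcg is 0.368 against 0.165 printed. Path rows free of cell conflicts also depart from the written prior, in both directions: the printed next dose is higher after 0/3 at 100 mcg and lower after 2/3 at 100 mcg. Neither version is therefore uniformly the more cautious.

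This rests on the literal specification: linear dose, 2.75 as a standard deviation, zero correlation, and full-weight fractional pseudo-patients. Confidence is high that the tables are not reproduced and low that any past dosing was affected. I ran no trial simulations, so Section 13.3.2 is not shown to be wrong; it simply cannot be tied to the printed prior. It must still be corrected, because the specification of the overdose-control model contradicts the output attributed to it.

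**What to change.** - Compare Tables 13-6 and 13-7 with the coded model in the simulation report, in particular standard deviation versus variance and the weight given to the pseudo-patients. Print the values actually used.
- Regenerate Tables 13-8 to 13-12 from that single model, and define the estimated-MTD column.
- Reconcile the 30 mcg row of Table 13-10, the 30 and 25 mcg rows and heading of Table 13-12, and the 195 mcg example in Section 6.10.1 with the regenerated output. No view is taken here on which dose is right.
- Confirm that Section 13.3.2, and the posterior carried into the IPE model, come from the same prior.

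The cost is a check against a report already on file and replacement appendix tables at the next amendment. Simulations need rerunning only if Section 13.3.2 came from a different prior.
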